8.1.2 STUDY DISCONTINUATION AND CLOSURE

This study may be temporarily suspended or prematurely terminated if there is sufficient reasonable cause. Written notification, documenting the reason for study suspension or termination, will be provided by the suspending or terminating party to regulatory authorities. If the study is prematurely terminated or suspended, the Principal Investigator (PI) will promptly inform study subjects and the Institutional Review Board (IRB), will provide the reason(s) for the termination or suspension. Study subjects will be contacted, as applicable, and be informed of changes to study visit schedule.

Circumstances that may warrant termination or suspension include, but are not limited to:

- Determination of unexpected, significant, or unacceptable risk to subjects
- Demonstration of efficacy that would warrant stopping

- Insufficient compliance to protocol requirements
- Data that are not sufficiently complete and/or evaluable
- Determination that the primary endpoint has been met
- Determination of futility

Study may resume once concerns about safety, protocol compliance, and data quality are addressed, and satisfy the IRB.

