7 STATISTICAL CONSIDERATIONS

7.1 STATISTICAL HYPOTHESES

- Primary Efficacy Endpoint(s):
- Change in Aerobic Capacity [Time Frame: baseline]
 - All subjects will undergo a progressive peak oxygen assessment to determine aerobic capacity at the Lakeshore Foundation Exercise Physiology Facility. Subjects will be instructed to perform arm crank ergometer (Lode) at 10W for 2 min. Every 2 min thereafter, power output will be increased by 10W until voluntary fatigue. Peak aerobic power will be defined as VO₂ at the point of failure to maintain 60-65 rotations per minute.
- Change in Aerobic Capacity [Time Frame: 16weeks post training]
 - All subjects will undergo a progressive peak oxygen assessment to determine aerobic capacity at the Lakeshore Foundation Exercise Physiology Facility. Subjects will be instructed to perform arm crank ergometer (Lode) at 10W for 2 min. Every 2 min thereafter, power output will be increased by 10W until voluntary fatigue. Peak aerobic power will be defined as VO₂ at the point of failure to maintain 60-65 rotations per minute.
- Change in Muscular Strength [Time Frame: baseline]
 - Muscle Strength Assessment. Maximal load that can be lifted in one repetition (1RM) will be assessed in both limbs for chest press, elbow flexion, and shoulder flexion maneuvers.
- Change in Muscular Strength [Time Frame: 16weeks post]
 - Muscle Strength Assessment. Maximal load that can be lifted in one repetition (1RM) will be assessed in both limbs for chest press, elbow flexion, and shoulder flexion maneuvers.
- Change in Insulin Sensitivity [Time Frame: baseline]
 - Oral glucose tolerance test. Following an overnight fast each subject will consume a 75g oral glucose load within 5 min. Blood samples will be collected immediately before and 60, 90, and 120 min following glucose ingestion for measurement of serum glucose and serum insulin.
- Change in Insulin Sensitivity [Time Frame: 16weeks post training]
 - Oral glucose tolerance test. Following an overnight fast each subject will consume a 75g oral glucose load within 5 min. Blood samples will be collected immediately before and 60, 90, and 120 min following glucose ingestion for measurement of serum glucose and serum insulin.
- Change in Blood Lipids [Time Frame: baseline]
 - Laboratory analyses. Concentrations of blood lipids will be determined in the Core Laboratory of the CCTS, NORC, and DRC.
- Change in Blood Lipids [Time Frame: 16weeks post training]

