7.3 STATISTICAL ANALYSES

Descriptive statistics, such as means, standard deviations, and 95% confidence intervals, will be calculated for all study variables of interest. The primary method of analysis will be mixed models repeated measures analyses, such as repeated measures analysis of covariance. This will allow us to test the group, time, and group by time interaction effect simultaneously. An appropriate structure for the covariance matrix (e.g. the unstructured covariance matrix) will be selected for these models using the final data. The Tukey-Kramer multiple comparisons test will be used as the *post hoc* test of choice for these analyses. ***Biological variables, such as age, sex, race, and %fat, will be accounted for in these models (see Rigor and Reproducibility in Statistical Design and Power document for details)*** Overall comparisons between means of the two groups will be performed using the two-group t-test, and overall changes within groups will be examined using the paired t-test. Correlation analysis will be performed, with Pearson correlation coefficients being calculated for pairs of continuous variables. Distributions of continuous variables will be examined for normality using box plots, stem-and-leaf plots, and normal probability plots; those deviating greatly from a normal distribution will be log transformed or analyzed using appropriate nonparametric tests such as the Wilcoxon rank-sum and signed-rank tests. Multiple imputation methods may be used to address missing data for variables with moderate amounts of missing data ($\geq 10\%$) and after examining whether data are missing completely at random (MCAR), at

random (MAR), or not at random (MNAR). Statistical tests will be two-sided and will be performed using a 5% significance level. SAS software, version 9.4 or later, will be used to conduct the statistical analyses.

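### Does section 8.1.2 open the door to early stopping for efficacy or futility without a rule in section 7?

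*Combined protocol and SAP*

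**What the plan says.** Section 8.1.2 opens its list with "Circumstances that may warrant termination or suspension include, but are not limited to". Three of its six entries concern results: "Demonstration of efficacy that would warrant stopping", "Determination that the primary endpoint has been met" and "Determination of futility". The others concern risk to subjects, compliance, and completeness of the data. The section requires written notification giving the reason for any suspension or termination, and requires that the IRB be told. It does not say who would judge efficacy or futility.

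Section 7 mentions no interim look. Section 7.1 lists six primary domains (aerobic capacity, muscular strength, insulin sensitivity, blood lipids, body composition, blood pressure) and ranks none of them first. Section 7.2 gives 40 participants. Section 7.3 says that the covariance structure "will be selected for these models using the final data", and sets one error level: "Statistical tests will be two-sided and will be performed using a 5% significance level". Section 2.1 gives 1:1 allocation and assessments at baseline and 16 weeks only.

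**The concern.** Each of the three grounds presupposes that someone has compared the arms before the study ends. A plan that intends this should say when the look happens, on which endpoint, against what boundary, and who makes it. Section 7 says none of these things, and the singular primary endpoint in 8.1.2 matches no single entry in 7.1.

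If an investigator used the efficacy ground and applied the only level the document states, the trial would have two chances at a 5% result and its type I error would exceed 5%. An estimate from a trial of this size stopped early for benefit would also tend to be too large. Futility stopping does not raise type I error, but an undefined rule can cost power.

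**Working it through.** **Inputs from the document.** 40 participants at 1:1, so 20 per arm (2.1, 7.2); two-sided 5% (7.3); no number or timing of looks anywhere. The only error figure stated is the 5% level, so there is no interim figure to reproduce.

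**The plan as written.** There is one analysis with critical value 1.96, so type I error per test = 2 × (1 − Φ(1.96)) = 5.0%. The list in 8.1.2 does not alter this.

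**One unplanned look, both analyses at 5% (assumed).** For one endpoint with a look at information fraction t, the two test statistics are bivariate normal under the null with correlation √t. Type I error = 1 − P(|Z₁| ≤ 1.96 and |Z₂| ≤ 1.96).

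| Look at t | Correlation √t | Type I error |
|---|---|---|
| none (as planned) | – | 5.0% |
| 0.25 | 0.500 | 9.1% |
| 0.50 | 0.707 | 8.3% |
| 0.75 | 0.866 | 7.3% |

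The result depends on the threshold as much as on the look. With an interim threshold of p < 0.001 at t = 0.5 and the final test at 5%, the same formula gives 5.02%. Section 8.1.2 does not say that p < 0.05 would count as demonstrated efficacy, so the 8.3% comes from carrying the final-analysis level over to a look the plan does not contain.

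**Exaggeration (assumed look at 10 per arm, two-sample t-tests, 400,000 simulated trials, effects in SDs of the analysed outcome).**

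| True effect | Stopped for benefit | Mean estimate if stopped | Mean over all trials with the look | Mean of significant results at 20 per arm, no look |
|---|---|---|---|---|
| 0.5 | 18% | 1.11 | 0.56 | 0.83 |
| 0.8 | 39% | 1.21 | 0.88 | 0.96 |

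The large values belong only to the minority of trials that stop. Over all trials the bias is 0.56 − 0.5 = 0.06 SD and 0.88 − 0.8 = 0.08 SD. Selecting significant results overstates a true 0.5 SD as 0.83 SD at 20 per arm with no look at all.

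**Futility (assumed rule: stop if interim p ≥ 0.5 at 10 per arm).** Type I error falls to 4.6%. Power at 0.8 SD goes from 69.3% to about 66.8%, a loss of about 2.5 points.

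**Is a look intended?** The text suggests not.
- Sections 2.1 and 4.1.1 have no assessment between baseline and week 16.
- Section 7.3 refers to the final data.
- The resumption sentence closing 8.1.2 deals with safety, compliance and data quality, and passes over efficacy and futility.
- Neighbouring sections carry other wording that does not fit an exercise trial: a package insert and death from anaphylaxis (6.2.4), a study product (6.2.2.2, 6.2.3), pharmacy records and an otolaryngology office (8.1.3).

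The stopping list reads as general text of the same kind.

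**The case for a change.** The best case for acting is that the permission stands as written, whatever its origin. No independent monitoring body is named, nothing in the document forbids comparing the arms early, and the list is open-ended. If no look is intended, removing three entries and adding a sentence to 7.3 would cost almost nothing. If one is intended, the plan is incomplete.

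The textual part of this stands: 8.1.2 and section 7 do not match, and the primary endpoint is not identifiable. The case for a change is weaker. The planned analysis and its error rate would be the same with or without the entries. The inflation comes only from trials that stop at the look, and 8.1.2 requires a written reason for stopping, so a reader would know and could discount the result.

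A blanket ban on comparing any efficacy endpoint before data lock would also have a cost. Blood pressure is one of the six listed efficacy domains, so read literally the ban would block a between-arm safety review of it. Removing futility gives up an option that does not raise type I error, and whether to keep it is the sponsor's choice. The lack of ranking among the six primaries is a separate matter that editing 8.1.2 would not settle.

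**Conclusion.** This is a minor inconsistency of wording and calls for no change to the plan. With one final analysis, as section 7.3 foresees, type I error per test is 5.0% and the estimates are unaffected by anything in 8.1.2. The rise to about 8.3% (7.3% to 9.1% over looks from three quarters to one quarter of the data) requires three things the document does not provide: an interim efficacy comparison, a 5% threshold for it, and a decision to stop on it. An analyst following section 7 would run one analysis after the week-16 data are in. The conclusion rests on no look being made. If the sponsor did intend one, its endpoint, timing, boundary and reviewer would have to be set out before any comparison of the arms.

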8.1.3 CONFIDENTIALITY AND PRIVACY

Subject confidentiality and privacy is strictly held in trust by the participating investigators and their staff. Therefore, the study protocol, documentation, data, and all other information generated will be held in strict confidence. No information concerning the study or the data will be released to any unauthorized third party without prior written approval of the Principal Investigator.

All research activities will be conducted in as private a setting as possible.

Representatives of the Institutional Review Board (IRB) may inspect all documents and records required to be maintained by the investigator, including but not limited to, medical records (office, clinic, or hospital) and pharmacy records for the subjects in this study. The clinical study site will permit access to such records.

The study subject's contact information will be securely stored at each clinical site for internal use during the study. At the end of the study, all records will continue to be kept in a secure location for as long a period as dictated by the reviewing IRB and/or Institutional policies.

Study subject research data, which is for purposes of statistical analysis and scientific reporting, will be stored at the UAB Department of Otolaryngology research office. This will not include the subject's contact or identifying information. Rather, individual subjects and their research data will be identified by a unique study identification number. The study data entry and study management systems used by research staff will be secured and password protected.

8.1.4 QUALITY ASSURANCE AND QUALITY CONTROL

The site will perform internal quality management of study conduct, data collection, documentation and completion. Quality control (QC) procedures will be completed by the Data Manager during data entry into the appropriate CRF. Any missing data or data anomalies will be communicated to the Study Coordinator for clarification/resolution.

Following written Standard Operating Procedures (SOPs), the monitors will verify that the clinical trial is conducted and data are generated are collected, documented (recorded), and reported in compliance with the protocol, International Conference on Harmonisation Good Clinical Practice (ICH GCP), and applicable regulatory requirements.

The site will provide direct access to all trial related sites, source data/documents, and reports for the purpose of monitoring and inspection by local and regulatory authorities.

8.1.5.1 DATA COLLECTION AND MANAGEMENT RESPONSIBILITIES

Data collection is the responsibility of the clinical trial staff at the site under the supervision of the Principal Investigator. The Principal Investigator is responsible for ensuring the accuracy, completeness, legibility, and timeliness of the data reported.

All source documents should be completed in a neat, legible manner to ensure accurate interpretation of data.

Hard copies of source document worksheets will be used for recording data for each subject enrolled in the study. Data recorded in the case report form (CRF) derived from source documents should be consistent with the data recorded on the source documents.

8.1.5.2 STUDY RECORDS RETENTION

Study documents should be retained for a minimum of 3 years after the completion of the study. These documents should be retained for a longer period, however, if required by local regulations.

8.1.6 PROTOCOL DEVIATIONS

A protocol deviation is any noncompliance with the clinical trial protocol requirements. The noncompliance may be either on the part of the subject, the investigator, or the study site staff. As a result of deviations, corrective actions are to be developed by the site and implemented promptly.

These practices are consistent with ICH GCP:

- 4.5 Compliance with Protocol, sections 4.5.1, 4.5.2, and 4.5.3
- 5.1 Quality Assurance and Quality Control, section 5.1.1
- 5.20 Noncompliance, sections 5.20.1, and 5.20.2.

It is the responsibility of the Principal Investigator to use continuous vigilance to identify and report deviations within 10 working days of identification of the protocol deviation. Protocol deviations must be sent to the reviewing Institutional Review Board (IRB) per their policies. The Principal Investigator is responsible for knowing and adhering to the reviewing IRB requirements.

8.1.7 CONFLICT OF INTEREST POLICY

The independence of this study from any actual or perceived influence, such as by the pharmaceutical industry, is critical. Therefore, any actual conflict of interest of persons who have a role in the design, conduct, analysis, publication, or any aspect of this trial will be disclosed and managed. Furthermore, persons who have a perceived conflict of interest will be required to have such conflicts managed in a way that is appropriate to their participation in the design and conduct of this trial.

8.2 ABBREVIATIONS

AE	Adverse Event
ANCOVA	Analysis of Covariance
CFR	Code of Federal Regulations
CONSORT	Consolidated Standards of Reporting Trials
CRF	Case Report Form
DHHS	Department of Health and Human Services
GCP	Good Clinical Practice
HIPAA	Health Insurance Portability and Accountability Act
ICH	International Conference on Harmonisation
ICMJE	International Committee of Medical Journal Editors
IRB	Institutional Review Board
LSMEANS	Least-squares Means
NCT	National Clinical Trial
NIH	National Institutes of Health
OHRP	Office for Human Research Protections
PI	Principal Investigator
QA	Quality Assurance
QC	Quality Control
SAE	Serious Adverse Event
SAP	Statistical Analysis Plan
SOA	Schedule of Activities
SOP	Standard Operating Procedure
UP	Unanticipated Problem
US	United States
